Objectives: Primary: 
To evaluate the effect of ALN-PCSSC treatment on LDL-C levels at Day 180. Secondary: 
To evaluate the effect of ALN-PCSSC on the following:
LDL-C levels at Day 90LDL-C levels at other time pointsPCSK9 levels over timeOther lipids, lipoproteins, apolipoproteinsProportion of subjects achieving prespecified global lipid guidelinesIndividual responsiveness to different dosesDuration of lipid-lowering effect of different dosesSafety and tolerability profile of ALN-PCSSC Exploratory: 
To collect/evaluate the effect of ALN-PCSSC on the following:
Cardiovascular (CV) events such as CV death, non-fatal myocardial infarction (MI), resuscitated cardiac arrest, and non-fatal stroke (ischemic and hemorrhagic)Evaluation of anti-drug antibodies (ADA) for the investigational product Methodology: This study will be a Phase II, placebo-controlled, double-blind, randomized trial in 480 subjects with atherosclerotic cardiovascular disease (ASCVD) or ASCVD-risk equivalents (eg, diabetes and familial hypercholesterolemia) and elevated LDL-C despite maximum tolerated dose of LDL-C lowering therapies to evaluate the efficacy, safety, and tolerability of ALN-PCSSC injection(s). Subjects will be screened and 480 eligible subjects will be randomized: 60 subjects per each of six ALN-PCSSC dose groups plus 120 subjects total across the placebo groups (20 subjects each to match each of the six drug dose groups). Treatment allocation will be stratified by country and by current use of statins or other lipid-modifying therapies. Each subject will either receive either one or two injections on Day 1 only or a single injection on Day 1 and a second injection on Day 90 of blinded ALN-PCSSC or placebo.

Formation of ADA will be assessed on Day 1 (prior to and 4 hours after the injection) and on Days 30, 60, 90, 120, 150, 180 (Days 150 and 180 only in subjects who receive a second dose of study drug), and 210 or until any ADA response becomes negative within the study duration. For subjects in whom LDL-C levels have not returned to >80% of baseline values, formation of ADA will also be assessed either when LDL-C has returned to normal limits or at the 1-year follow-up visit.

The independent Data Monitoring Committee (DMC) will review safety data beginning after the first 40 subjects receive the first injection of ALN-PCSSC or placebo and complete the Day 14 follow-up visit. Thereafter the DMC will review safety data every 2 months until the end of the trial. A recommendation may be taken to stop or amend the study at any of these reviews.

On Day 1, all eligible subjects will be randomized and receive the first SC administration of ALN-PCSSC or placebo. After first study drug administration, the subject will be observed in the clinic for at least 4 hours post injection before being discharged. Subjects will return at Day 14 and Day 30 and then at monthly intervals for 6 months. Subjects randomized to receive a second dose of study drug will receive the second injection of ALN-PCSSC or placebo at the Day 90 visit and will have an extra visit on Day 104 (14 days after the second dose on Day 90).

Efficacy assessments will include the measure the effects of ALN-PCSSC on levels of LDL-C lipids and lipoproteins including total cholesterol, triglycerides, high-density lipoprotein cholesterol (HDL-C), non-HDL-C, very low-density lipoprotein cholesterol (VLDL-C), apolipoprotein A1 (Apo-A1), apolipoprotein B (ApoB), lipoprotein(a) [Lp(a)], high sensitivity C-reactive protein (hsCRP), and PCSK9.

End of study (EOS) evaluations will be conducted at the EOS visit (Day 210).

Subjects whose LDL-C levels have returned to baseline levels and who have completed the study to Day 210 will be given the opportunity to enroll in a separate long-term extension study to collect long-term efficacy and safety data.

Any subjects in whom LDL-C levels have not returned to >80% of baseline values will continue to be followed as part of this study until either this level has been reached or until a maximum of Day 360 at which point they will be given the opportunity to enroll in the long-term extension study. At each visit, LDL-C levels, adverse events (AEs), serious adverse events (SAEs), concomitant medications, and safety laboratory assessments will be collected.

Number of Subjects: 480 planned; at least 400 evaluable

Diagnosis and Main Criteria for Selection:

Subjects may be included if they meet all of the following inclusion criteria prior to randomization:

1. Male or female subjects ≥ 18 years of age.
2. History of ASCVD or ASCVD-risk equivalents (symptomatic atherosclerosis, Type 2 diabetes, familial hypercholesterolemia, including subjects whose 10-year risk of a cardiovascular [CV] event assessed by Framingham Risk Score* or equivalent has a target LDL-C of < 100 mg/dL).
3. Serum LDL-C ≥ 1.8 mmol/L (≥ 70 mg/dL) for ASCVD subjects or ≥ 2.6 mmol/L (≥ 100 mg/dL) for ASCVD-risk equivalent subjects at screening.
4. Fasting triglyceride < 4.52 mmol/L (< 400 mg/dL) at screening.
5. Calculated glomerular filtration rate > 30 mL/min by estimated glomerular filtration rate (eGFR) using standardized local clinical methodology.
6. Subjects on statins should be receiving a maximally tolerated dose (investigator's discretion).
7. Subjects on lipid-lowering therapies (such as statin and/or ezetimibe) should be on a stable dose for ≥ 30 days before screening with no planned medication or dose change during study participation.
8. Willing and able to give informed consent before initiation of any study-related procedures and willing to comply with all required study procedures.

*By Framingham Risk Score $> 20\%$

Subjects will be excluded from the study if any of the following exclusion criteria apply immediately prior to randomization:

1. Any uncontrolled or serious disease, or any medical or surgical condition, that may either interfere with participation in the clinical study, and/or put the subject at significant risk (according to investigator's [or delegate] judgment) if he/she participates in the clinical study.
2. An underlying known disease, or surgical, physical, or medical condition that, in the opinion of the investigator (or delegate) might interfere with interpretation of the clinical study results.
3. New York Heart Association (NYHA) class II, III or IV heart failure or last known left ventricular ejection fraction <30%.
4. Cardiac arrhythmia within 3 months prior to randomization that is not controlled by medication or via ablation.
5. Any history of hemorrhagic stroke.
6. Major adverse cardiac event within 6 months prior to randomization.
7. Uncontrolled severe hypertension: systolic blood pressure >180 mmHg or diastolic blood pressure >110 mmHg prior to randomization despite anti-hypertensive therapy.
8. Poorly controlled Type 2 diabetes, ie, glycated hemoglobin A1c (HbA1c) >10.0% prior to randomization.
9. Active liver disease defined as any known current infectious, neoplastic, or metabolic pathology of the liver or unexplained alanine aminotransferase (ALT), aspartate aminotransferase (AST), elevation >2x the upper limit of normal (ULN), or total bilirubin elevation >1.5x ULN at screening confirmed by a repeat measurement at least 1 week apart.
10. Serious comorbid disease in which the life expectancy of the subject is shorter than the duration of the trial (eg, acute systemic infection, cancer, or other serious illnesses). This includes all cancers with the exception of treated basal-cell carcinoma occurring >5 years before screening.
11. Females who are pregnant or nursing, or who are of childbearing potential and unwilling to use at least two methods of contraception (oral contraceptives, barrier methods, approved contraceptive implant, long-term injectable contraception, intrauterine device or tubal litigation)**. Women who are >2 years postmenopausal defined as ≥ 1 year since last menstrual period AND if <55 years old with a negative pregnancy test within 24 hours of randomization or surgically sterile are exempt from this exclusion.
12. Males who are unwilling to use an acceptable method of birth control during the entire study period (ie, condom with spermicide).
13. Known history of alcohol and/or drug abuse with the last 5 years.
14. Treatment with other investigational medicinal products or devices within 30 days or five half-lives, whichever is longer.
15. Use of other investigational medicinal products or devices during the course of the study.
16. Any condition that according to the investigator could interfere with the conduct of the study, such as but not limited to:
 - a. Inappropriate for this study, including subjects who are unable to communicate or to cooperate with the investigator.
 - b. Unable to understand the protocol requirements, instructions and study-related restrictions, the nature, scope, and possible consequences of the study (including subjects whose cooperation is doubtful due to drug abuse or alcohol dependency).
 - c. Unlikely to comply with the protocol requirements, instructions, and study-related restrictions (eg, uncooperative attitude, inability to return for follow-up visits, and improbability of completing the study).
 - d. Have any medical or surgical condition, which in the opinion of the investigator would put the subject at increased risk from participating in the study.
 - e. Involved with, or a relative of, someone directly involved in the conduct of the study.
 - f. Any known cognitive impairment (eg, Alzheimer's disease).
17. Previous or current treatment (within 90 days of screening) with monoclonal antibodies directed towards PCSK9.

**For the entire duration of the study

Subjects excluded for any of the above reasons may not be re-screened for participation at any time if the exclusion characteristic has changed.

Test Product, Dose and Mode of Administration: ALN-PCSSC will be administered as either a single SC injection (doses: 200 mg, 300 mg), or two injections (dose: 500 mg) on Day 1 or two SC injections (doses: 100 mg, 200 mg, or 300 mg) on Day 1 and Day 90.

Duration of Treatment: The expected duration of the subjects' involvement in the study will be approximately 224 days which includes screening, study drug administration, the course of single or multiple injections, and the follow-up period to Day 210; if additional follow-up is necessary, the expected maximum duration of involvement in the study will be 374 days.

Single Dose (one or two injections on Day 1):

- Screening: Day -14 to -1
- Randomization, initiation of study drug: Day 1
- Treatment Phase: Day 1
- Follow-up:
 - Follow-up: Days 2 to 210; EOS on Day 210
 - Additional Follow-Up (for subjects in whom LDL-C levels have not returned to >80% of baseline values; subjects will return each month for follow-up until this level has been reached or until Day 360): Days 240, 270, 300, 330, and 360

Two Doses (one injection each on Day 1 and Day 90):

- Screening: Day -14 to -1
- Randomization, initiation of study drug: Day 1
- Treatment Phase: Day 1 to Day 90
- Follow-up:
 - Follow-up: Days 91 to 210; EOS on Day 210
 - Additional Follow-Up (for subjects in whom LDL-C levels have not returned to >80% of baseline values; subjects will return each month for follow-up until this level has been reached or until Day 360): Days 240, 270, 300, 330, and 360

Reference Therapy, Dose, and Mode of Administration: Placebo will be administered as either one or two SC injections of saline solution. Placebo volume will be matched to test product volume within each dose and injection regimen but not between injection regimens. For example, the placebo group for the 200 mg dose will receive 1.0 mL of placebo whereas the placebo group for the 300 mg dose will receive 1.5 mL of placebo.

Criteria for Evaluation:

Efficacy:

Primary Endpoint:

- Percentage change in LDL-C from baseline to Day 180

Secondary Endpoints:

- Percentage change in LDL-C from baseline to Day 90
- Percentage change in LDL-C from baseline to Days 14, 30, 60, 104, 120, 150, and 210
- Proportion of subjects in each group with LDL-C greater than 80% of the baseline value at Day 180 and Day 210
- Duration of time on treatment for subjects to return to 80% of baseline or greater LDL-C or PCSK9 protein
- Individual responsiveness defined as the number of subjects reaching on treatment LDL-C levels of

<25 mg/dL, <50 mg/dL, <70 mg/dL, and <100 mg/dL at Days 90, 120, and 180

- Proportion of subjects in each group with greater or equal to 50% LDL-C reduction from baseline at Days 90, 120, and 180
- Percentage change in PCSK9 levels from baseline to Days 14, 30, 60, 90, 104, 120, 150, 180, and 210
- Percentage change in other lipids, lipoproteins, apolipoproteins, from baseline at each subsequent visit to Day 210
- Proportion of subjects in each group who attain global lipid modification targets for their level of ASCVD risk

Safety: AEs, SAEs, vital signs, clinical laboratory values (hematology, coagulation testing, chemistry, and urinalysis), and electrocardiograms (ECGs) will be collected at specified visits through the EOS visit (Day 210). AEs, SAEs, and clinical laboratory values will continue to be assessed during the additional monthly follow-up visits (for subjects in whom LDL-C levels have not returned to >80% of baseline values). Cardiovascular events will be reported as AEs for the compilation of information on CV events such as CV death, non-fatal MI, resuscitated cardiac arrest, and non-fatal stroke (ischemic and hemorrhagic). In addition, ADA will be evaluated for the investigational product.

Statistical Methods:

Sample Size and Power

The sample size calculation was performed with the assumption (which was based on the observed results from a Phase I trial) that the difference in change from baseline between the active dose groups and the placebo group for LDL-C will be no less than 30 mg/dL, with a standard deviation of 20 mg/dL, using a Dunnet multiple t-test procedure for six comparisons.

Assuming about a 15% drop out rate, the sample size will be approximately 100 evaluable subjects total across the placebo groups and approximately 50 subjects in each of six ALN-PCSSC dose groups. This sample size of at least 400 evaluable subjects will provide more than 90% power to detect a 30% reduction of LDL-C levels in at least one ALN-PCSSC dose group.

Primary Endpoint Analysis:

Two sample t-tests will be performed to test the superiority of any dosing group over placebo. A Dunnet multiple t-test procedure will be applied to adjust for multiple comparisons with six different dosing regimens.

Secondary and Exploratory Endpoint Analysis:

The analysis of the secondary and exploratory endpoints will be descriptive.

Interim Analysis:

An interim analysis of lipids and PCSK9, unblinded by dose cohort only, will be prepared upon completion of Day 90 by the Statistical Reporting Organization. The interim analysis will be performed for all subjects completing Day 90 and these data will be used to help select the ALN-PCSSC dose for subsequent clinical trials.

TABLE OF CONTENTS

PROTOCOL SYNOPSIS	3
LIST OF ABBREVIATIONS	13
1. INTRODUCTION	15
1.1. Background	15
1.1.1. Disease Overview	15
1.1.2. PCSK9 Biology and Target Rationale	15
1.1.3. Mechanism of RNA Interference	16
1.2. ALN-PCSSC, an RNAi Therapeutic for Hypercholesterolemia	17
1.2.1. Preclinical Studies	17
1.2.2. Clinical Studies	18
1.2.3. Known and Potential Risks and Benefits	18
1.3. Study Rationale	19
1.3.1. Study Rationale	19
1.3.2. Dose Rationale	19
1.4. Study Population	19
2. TRIAL OBJECTIVES AND PURPOSE	20
2.1. Primary Objective	20
2.2. Secondary Objectives	20
2.3. Exploratory Objectives	20
3. TRIAL DESIGN	21
3.1. Type/Design of Trial	21
3.2. Schematic Diagram of Trial Design	22
3.2.1. One Dose (one or two injections on Day 1)	22
3.2.2. Two Doses (one injection each on Day 1 and Day 90)	23
3.3. Primary Endpoint(s)	23
3.4. Secondary Endpoints	23
3.5. Exploratory Endpoint(s)	24
3.6. Measures to Minimize/Avoid Bias	24
3.6.1. Blinded Study Where Pharmacist is Unblinded	24
4. SUBJECT POPULATION	25
4.1. Number of Subjects	25

4.2.	Inclusion Criteria	25
4.3.	Exclusion Criteria	25
4.4.	Withdrawal Criteria	27
4.4.1.	Withdrawal from Study Medication	28
5.	TREATMENT OF SUBJECTS	29
5.1.	Study Medications	29
5.1.1.	ALN-PCSSC	29
5.1.2.	Placebo	29
5.1.3.	Packaging and Labeling	29
5.1.4.	Storage	29
5.1.5.	Accountability	29
5.2.	Concomitant Medications	30
5.2.1.	Prohibited Concomitant Medications	30

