4.2. Inclusion Criteria

Subjects may be included in the study if they meet all of the following criteria:

1. Male or female subjects ≥ 18 years of age.
2. History of ASCVD or ASCVD-risk equivalents (symptomatic atherosclerosis, Type 2 diabetes, familial hypercholesterolemia, including subjects whose 10-year risk of a cardiovascular [CV] event assessed by Framingham Risk Score* or equivalent has a target LDL-C of < 100 mg/dL).
3. Serum LDL-C ≥ 1.8 mmol/L (≥ 70 mg/dL) for ASCVD subjects or ≥ 2.6 mmol/L (≥ 100 mg/dL) for ASCVD-risk equivalent subjects at screening.
4. Fasting triglyceride < 4.52 mmol/L (< 400 mg/dL) at screening.
5. Calculated glomerular filtration rate > 30 mL/min by estimated glomerular filtration rate (eGFR) using standardized local clinical methodology.
6. Subjects on statins should be receiving a maximally tolerated dose (investigator's discretion).
7. Subjects on lipid-lower therapies (such as statin and/or ezetimibe) should be on a stable dose for ≥ 30 days before screening with no planned medication or dose change during study participation.
8. Willing and able to give written and informed consent before initiation of any study-related procedures and willing to comply with all required study procedures.

*By Framingham Risk Score $> 20\%$

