13. Known history of alcohol and/or drug abuse within the last 5 years.
14. Treatment with other investigational medicinal products or devices within 30 days or five half-lives, whichever is longer.
15. Use of other investigational medicinal products or devices during the course of the study.
16. Any condition that according to the investigator could interfere with the conduct of the study, such as but not limited to:
 - a. Inappropriate for this study, including subjects who are unable to communicate or to cooperate with the investigator

- b. Unable to understand the protocol requirements, instructions and study-related restrictions, the nature, scope, and possible consequences of the study (including subjects whose cooperation is doubtful due to drug abuse or alcohol dependency)
- c. Unlikely to comply with the protocol requirements, instructions, and study-related restrictions (eg, uncooperative attitude, inability to return for follow-up visits, and improbability of completing the study)
- d. Have any medical or surgical condition, which in the opinion of the investigator would put the subject at increased risk from participating in the study
- e. Involved with, or a relative of, someone directly involved in the conduct of the study
- f. Any known cognitive impairment (eg, Alzheimer's disease)

17. Previous or current treatment (within 90 days of screening) with monoclonal antibodies directed towards PCSK9.

**For the entire duration of the study

Subjects excluded for any of the above reasons may not be re-screened for participation at any time if the exclusion characteristic has changed.

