5.2. Concomitant Medications

5.2.1. Prohibited Concomitant Medications

The following medications/treatments are not permitted to be added during the study:

- Medications used to lower LDL-C (eg, statins, ezetimibe, lomitapide, mipomersen, niacin, colesevelam, bile acid absorption inhibitors, monoclonal antibodies for PCSK9).

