5.2.2. Permitted Concomitant Medication(s)

The following medications/treatments are permitted during the study:

- Hormone replacement therapy
- Lipid-lower medications; subjects on lipid-lower medications (such as statins and/or ezetimibe) should be on a stable dose for ≥ 30 days before screening with no planned medication or dose change during study participation
- Prescription medications prescribed to treat pre-existing medical conditions such as diabetes and hypertension
- Prescription or nonprescription medications, when necessary to treat an AE, and at the discretion of the investigator

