10.2. Randomization

Subjects will be screened and 480 eligible subjects will be randomized by the IWRS system: 60 subjects per each of six ALN-PCSSC treatment groups plus 120 subjects total across the placebo groups (20 subjects each to match each of the six drug groups). Treatment will be stratified by country and by current use of statins or other lipid-modifying therapies. Each subject will either receive either one or two injections on Day 1 only or a single injection on Day 1 and a second injection on Day 90 of blinded ALN-PCSSC or placebo.

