10.3.3. Analysis Windows and Baseline

The observational period for each subject includes the screening period (from Day -14 to Day -1), the EOS visit (Day 210 or withdrawal date). The time at which LDL-C levels have returned to >80% of baseline values will be the last observation. Any lab results collected after the last observation will not be included in the planned efficacy analysis. Safety events after the last observation, even if collected on the eCRF, will not be included in the planned statistical analysis. However, all data, including that reported after the defined observational period, will be included in the subject data listings.

Unless otherwise specified, for evaluations that are collected at multiple occasions prior to initiation of study drug, the last evaluation will be considered the "Baseline" evaluation for analysis.

Two samples for lipids and PCSK9 will be taken prior to initiation of study drug (one at screening and one prior to randomization on Day 1). The average value of the two samples will be used as the baseline evaluation.

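### The 30-day stability rule covers only current lipid-lowering therapy, so a subject who stopped a statin just before screening can enter with a baseline LDL-C that is still rising. This mainly affects the duration and responder summaries, not the primary test.

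*Protocol*

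**What the plan says.** Criterion 7 in the Protocol Synopsis states: "Subjects on lipid-lowering therapies (such as statin and/or ezetimibe) should be on a stable dose for ≥ 30 days before screening". Section 4.2 repeats it almost word for word, and section 5.2.2 carries the same condition for permitted medication. The rest of the sentence rules out planned changes, but only from enrolment onwards. Criterion 6, on maximally tolerated dosing, is likewise limited to subjects taking a statin.

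The only look-back for an approved lipid-lowering class is exclusion 17: "Previous or current treatment (within 90 days of screening) with monoclonal antibodies directed towards PCSK9". Exclusion 14 concerns investigational products and devices.

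Subjects not on therapy are expected, since section 10.2 says: "Treatment will be stratified by country and by current use of statins or other lipid-modifying therapies".

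On baseline lipids and PCSK9, section 10.3.3 takes one sample at screening and one on Day 1: "The average value of the two samples will be used as the baseline evaluation". Screening runs from Day -14 to Day -1, so the two samples are at most about 14 days apart. SAP 5.3.3 keeps the average, and adds rules for one sample or more than two.

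Section 5.2.1 introduces its list of LDL-C-lowering drugs with: "The following medications/treatments are not permitted to be added during the study".

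**The concern.** A subject who gave up a statin a week before screening is not on it, so criterion 7 does not reach that subject and no exclusion does. LDL-C is then moving towards its off-drug level while both baseline samples are drawn. Section 5.2.1 bars adding the drug back, so the rise continues after randomisation.

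Baseline is the denominator of the primary endpoint (percentage change at Day 180) and of the 50%-reduction responder endpoint. It also sets the 80% level used for duration of effect and for the proportions at Days 180 and 210. A low baseline moves all of these in a known direction.

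The duration endpoint has a further link. Under sections 3.1 and 6, follow-up after Day 210 continues only until LDL-C exceeds 80% of baseline, and section 10.3.3 makes that crossing the last observation for efficacy. An early crossing caused by a low baseline may therefore not be recoverable from later data. Duration is a secondary objective, and the results are meant to guide dose selection for later trials.

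**Working it through.** **The plan's own figure.** Inputs from Protocol 10.1: difference 30 mg/dL, SD 20 mg/dL, 100 pooled placebo and 50 per active group, Dunnett for six comparisons. Alpha is not stated there; two-sided familywise 0.05 is assumed. The simulated Dunnett critical value (correlation 1/3, 393 df) is 2.616. The noncentrality is 30 / (20 × √(1/50 + 1/100)) = 8.66. Power for one contrast is above 99.9%, so the stated figure of more than 90% holds as a lower bound.

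**One affected subject.** Let b be the measured baseline as a share of settled off-drug LDL-C. Then b = 1 − r(1 − f), where r is the reduction the stopped drug had given and f is the share of the rebound complete at the averaged baseline. Neither is in the documents. Assumed ranges are r = 0.2-0.4 and f = 0.25-0.75, giving b = 0.70-0.95. The midpoint (0.3, 0.5) gives b = 0.85, and (0.4, 0.5) gives b = 0.80. The true drug effect is assumed to be -50%.

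- Placebo change = 1/b − 1
- Drug change = 0.5/b − 1
- Drug effect still present at 80% of baseline = 1 − 0.8b
- True reduction needed to count as a 50% responder = 1 − 0.5b

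| b | Placebo | Drug | Difference (points) | Effect left at 80% level | Needed for 50% response |
|---|---|---|---|---|---|
| 1 | 0% | -50% | -50 | 20% | 50% |
| 0.85 | +17.6% | -41.2% | -58.8 | 32% | 57.5% |
| 0.80 | +25.0% | -37.5% | -62.5 | 36% | 60% |

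Over b = 0.95 to 0.70, placebo reads +5% to +43% and drug -47% to -29%.

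**Duration in one affected subject.** Assume a 50-60% reduction at Day 84, 40% at Day 140 (Protocol 1.2.2 gives about 40% at 140 days) and linear waning. Crossing day = 84 + (peak − effect left) / ((peak − 0.40)/56). With b = 1 this is Day 196-252, with b = 0.85 Day 162-185, and with b = 0.80 Day 151-162.

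**Group level, primary contrast.** Let p be the share affected, assumed 5-10%. Difference = −50(1 − p) − 50p/b.

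- b = 0.85: -50.4 (p = 0.05), -50.9 (p = 0.10)
- b = 0.80: -50.6 (p = 0.05), -51.3 (p = 0.10)

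**Precision of that contrast.** The protocol's SD of 20 is in mg/dL, and no SD for percentage change is given; 20 percentage points is assumed. Each arm's variance becomes 400 + p(1 − p) × shift², with shifts of 25 (placebo) and 12.5 (drug) at b = 0.80, or 17.6 and 8.8 at b = 0.85. The unaffected contrast variance is 400/100 + 400/50 = 12.

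- b = 0.80, p = 0.10: 456.25/100 + 414.06/50 = 12.84, and 12/12.84 is a loss of 6.6%
- b = 0.80, p = 0.05: 12.45, loss 3.6%
- b = 0.85, p = 0.10: 12.42, loss 3.4%
- b = 0.85, p = 0.05: 12.22, loss 1.8%

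At the outer corners (b = 0.95 with p = 0.05; b = 0.70 with p = 0.10) the difference is -50.1 and -52.1, and the loss 0.2% and 17%. Power stayed above 99.9% in every scenario run, including b = 0.70 with 20% affected and a true effect of only -30%.

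**Group level, descriptive endpoints.** With about 50 evaluable subjects per group, 5-10% is 50 × 0.05 = 2.5 to 50 × 0.10 = 5 subjects. A group proportion can therefore move by at most 5-10 percentage points.

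**The case against.** The surrounding text describes a population already on maximum tolerated therapy (Synopsis, 1.4, 3.1), and 1.2.3 says subjects receive guideline-based background therapy. Exclusion 16 lets an investigator refuse anyone judged unsuitable. Prior medications are collected and summarised, so recent stoppers could be found if stop dates are recorded. This narrows the gap without closing it: the descriptions are not eligibility criteria, and neither exclusion 16 nor any other criterion mentions a recent stop.

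The stronger objections concern size, and they stand:

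- **Prevalence.** A reader might infer from sections 1.1.1 and 1.2, which discuss statin intolerance, that recent stoppers will be common. Those sections do not say when intolerant patients stopped; many may have been off statins for years.
- **Timing.** Assume 30-50% of LDL-C reduction is lost on stopping, the half-time of the rise is 4-14 days, and the samples are 3-14 days apart. Then b is 0.56-0.86 for a stop one day before screening and 0.88-1.00 at 28 days. The problem sits mainly in stops within about two weeks of screening.
- **Precision.** A reader might look at the placebo arm alone at b = 0.80 and infer a 7-12% loss (400/429.7 and 400/456.25). The test compares placebo with an active arm whose shift is half as large, so that figure overstates the loss.
- **Ezetimibe.** A reader might infer that someone who dropped a statin but kept a stable ezetimibe dose clearly qualifies. That subject is on lipid-lowering therapy, so criterion 7 applies, and the recent change can fairly be read as failing it. The case is ambiguous.

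**Conclusion.** The gap is real: followed as written, the criteria admit recent stoppers with an unsettled baseline. Stratification does not separate them, because a recent stopper on no other lipid drug falls in the same stratum as long-term non-users.

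The consequence is limited. In an affected subject the percentage change, responder status and duration are misread, and the by-group duration, 80%-of-baseline and 50%-responder summaries have no placebo correction. A reader might infer that the primary result is compromised. The documents do not support that: randomisation balances recent stoppers in expectation, the contrast shifts by about one point under the main assumptions (5-10% affected, b of 0.80-0.85, true effect -50%), and power is not threatened. Prevalence, rebound speed and the SD of percentage change are all assumptions. This is a cheap improvement, not a flaw that puts the trial's main conclusion at risk.

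**What to change.** Reword criterion 7 in the Synopsis and section 4.2, and the matching line in 5.2.2, to: *No lipid-lowering therapy started, stopped or changed in dose within 30 days before screening, and no such change planned during study participation.* This keeps the protocol's own 30-day period, extends it to stopped therapy, and settles the ezetimibe case. Under the rebound ranges above, most of the distortion is gone by then, though not all of it.

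The cost is one sentence in an amendment, with a few recent stoppers screened up to 30 days later. For anyone enrolled under the present wording, the SAP could add a sensitivity analysis leaving out subjects whose prior-medication record shows a recent stop, provided stop dates are held.
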